2 OBJECTIVES

The objective of the study is to evaluate and compare the performance of Alcon's Precision1 lens (P1) to clariti 1 day (C1D), when worn on a daily disposable modality over a period of approximately one week each. C1D is considered the study test lens. P1 will be the control lens.

The primary outcome variables of this study are:

- Subjective ratings for 'Lens handling for lens insertion' (0 - 10 integer scale) for TEST lens compared to CONTROL, collected at the 1-week visit reflecting on a 'typical day' experience during the study;
- Subjective ratings for 'Lens handling for lens removal' (0 - 10 integer scale) for TEST lens compared to CONTROL, collected at the 1-week visit reflecting on a 'typical day' experience.

The secondary outcome variables are:

- Centration (optimal, slight decentration, moderate decentration but not encroaching limbus, excessive & occasionally encroaching limbus), collected at dispense & 1-week visit;
- Post-blink movement in primary gaze, mm, collected at dispense & 1-week visit;

Participants will be randomized to wear either the test or the control lens first. All lenses will be worn in a daily disposable lens wear modality for one week (-1/+3 days). The study involve up to 5 scheduled visits. The study design is shown in Figure 1.

[figure not shown]

Figure 1: Study Design, visits 1 & 2 may be on a single day, also visits 3 & 4 may be on a single day.

Visit 1: Includes screening, baseline assessments, fitting of both study lenses.

Visit 2: Dispense lens pair #1 (either test or control lens, randomized).

Visit 3: 1-week follow-up assessment of lens pair #1

Visit 4: Dispense of lens pair #2 (either test or control lens)

Visit 5: 1-week follow-up assessment of lens pair #2 and study exit.

- Participants will complete the following in-office subjective ratings on paper using a numeric rating scale (0 – 10) at visits 3 and 5 for each lens type:
- Lens handling;
- [REDACTED]
- [REDACTED]
- [REDACTED]
- [REDACTED]

[REDACTED]

[REDACTED]

[REDACTED]

[REDACTED]

- [REDACTED]
- [REDACTED]
- [REDACTED]
- [REDACTED]

- [REDACTED]
- [REDACTED]
- [REDACTED]
- [REDACTED]
- [REDACTED]

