5.3.3 DISPENSING LENS TYPE #1 (VISIT 2)

The procedures to be performed are outlined below:

1. The participant will be assigned a randomization ID (by the research assistant) and the first pair (lens pair #1) of contact lenses (either test or control lens) will be selected according to the randomization table.
2. Lens pair #1 will be provided to participants in a manner which does not unmask the participant or investigator, as described in Section 5.2.4.
3. The participant will insert the lenses.
4. The contact lenses will be allowed to settle for 10 minutes.
5. [REDACTED]
 - [REDACTED]
 - [REDACTED]
6. [REDACTED]
 - [REDACTED]
8. Lens [REDACTED] fit will be assessed and graded according to the following grading scales:
 - a. [REDACTED]
 - b. [REDACTED]
 - c. Lens push-up tightness in primary gaze (0 – 100 scale);
 - d. Centration in primary gaze (scale: optimal, slight decentration, moderate decentration but not encroaching limbus, excessive & occasionally encroaching limbus);
 - e. Post-blink movement in primary gaze (mm);
 - f. [REDACTED]
9. Provide and explain to participant subjective at-home rating forms to be completed on Day 1, 3 and 5 after Visit 2 (i.e. Day 1 is the day after the dispensing visit). These forms will be completed just after lens insertion and just before lens removal. Ratings will include:
 - a. [REDACTED]
 - b. Ease of lens handling for lens insertion (0 – 10 integer scale);
 - c. [REDACTED]
 - [REDACTED]
 - [REDACTED]
 - [REDACTED]
 - [REDACTED]
 - [REDACTED]
 - [REDACTED]
 - i. Ease of lens handling for removal (0 – 10 integer scale).

- b) [REDACTED]
 - c) Lens push-up tightness in primary gaze (0 – 100 scale);
 - d) Centration in primary gaze (scale: optimal, slight decentration, moderate decentration but not encroaching limbus, excessive & occasionally encroaching limbus);
 - e) Post-blink movement in primary gaze (mm);
 - f) [REDACTED]
6. [REDACTED]
7. [REDACTED]
8. There will be a washout of 10 minutes after lens removal if Visit 4 is to be concurrent with this visit.

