12 STATISTICAL ANALYSIS AND DATA MANAGEMENT

12.1 STATISTICAL ANALYSIS

Primary comparisons will be between study lenses, however there are some variables collected over time with the same lens and this time comparison will be analysed (e.g. 'at-home ratings on Days 1, 3 and 5).

All data will be analyzed by CORE at the University of Waterloo. Unmasked data analysis will be conducted using Statistica, SPSS, or other appropriate software. Descriptive statistics will be provided on information regarding baseline variables (age, gender, refractive error distribution, etc.). Table 6 lists the main outcome variables and anticipated statistical procedures. All data will be tested for normality of distribution using Shapiro-Wilk tests.

Results for logMAR will be reported and analysed for binocular acuity and in some cases data of right eye only will be analysed and reported (e.g. lens fit variables, biomicroscopy).

Data from 'at-home' ratings Day 5 will be analysed to determine the mean 'cumulative comfort score', as described by Keir et al.³

A binomial test will be used to analyze the results for the count data of subjective preferences.

Table 6: Statistical analysis to be conducted

Variable	Analysis	Statistical test
Subjective ratings	Descriptive and other statistics	Mean, Median*, Standard Deviation, Minimum, Maximum, Frequency count
	Effect of treatment on outcome variable within subjects (comparison between study days) Effect of time on ratings (comparison over time)	Friedman Wilcoxon matched pairs test
Visual acuity; NITBUT; lens centration and movement; limbal, bulbar and tarsal redness; corneal and conjunctival staining	Descriptive statistics	Mean, Median*, Standard Deviation, Minimum, Maximum, Count
	Effect of treatment on outcome variable within subjects (comparison between study days)	RMANOVA Paired t-test

* For non-parametric data only

The critical alpha level for statistical significance will be set at 0.05, with no adjustments for multiple comparisons.

All participants who were evaluated will be included in the analysis, unless their removal is agreed by the sponsor due to protocol deviations and/or adverse events. In the event of missing data, individual data points will not be extrapolated from the collected data.

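### Friedman and RMANOVA in Table 6 use complete rows only, so one missed at-home form or fit visit drops a participant from that test (minor)

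*Combined protocol and SAP*

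**What the plan says.** Section 12.1 sets the analysis population: "All participants who were evaluated will be included in the analysis, unless their removal is agreed by the sponsor", the permitted grounds being protocol deviations and adverse events. On gaps it says: "In the event of missing data, individual data points will not be extrapolated from the collected data".

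Table 6 lists "Friedman Wilcoxon matched pairs test" for subjective ratings and "RMANOVA Paired t-test" for acuity, NITBUT, lens fit, redness and staining. Its status is given as: "Table 6 lists the main outcome variables and anticipated statistical procedures". Section 12.1 also says that some variables are followed over time within the same lens, with the at-home ratings as its example.

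The repeated data come from two sources:
- **At-home forms.** Section 5.3.3 has "subjective at-home rating forms to be completed on Day 1, 3 and 5 after Visit 2", and Section 5.3.5 and Table 3 repeat this for the second lens. That gives three forms per lens.
- **Lens fit.** Section 2 lists as a secondary outcome "Post-blink movement in primary gaze, mm, collected at dispense & 1-week visit", and centration on the same schedule. That gives two visits for each of two lenses, or four cells.

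The visible text does not say how a participant with some cells missing enters Friedman or RMANOVA. It names no available-data method and does not ask for the N of each test.

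**The concern.** Friedman ranks the occasions within each participant and needs every occasion. Classical RMANOVA needs every cell. Since the plan does not fill gaps, a participant with one gap leaves the whole test and the values that were recorded go unused there. That sits poorly with a statement that all evaluated participants are included.

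Two things are at stake. One is precision, in a study of about 28 to 31 people. The other is bias, should the gaps relate to how a participant's response differs between lenses or over time. Section 9 lists unacceptable comfort or vision, persistent symptoms and adverse events among the reasons for discontinuation, so such a link is possible. If the handling is not fixed in advance, it will be chosen during the analysis, which Section 12.1 describes thus: "Unmasked data analysis will be conducted using Statistica, SPSS, or other appropriate software".

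**Working it through.** **The plan's own figures.** Section 5.1.1 gives N = 47 for a difference of 0.8, SD 1.9, 80% power and two-sided alpha 0.05. Taking 1.9 as the SD of the paired difference, the noncentrality is (0.8/1.9) × √47 = 2.89 on 46 degrees of freedom, and power is 0.807. The figure reproduces, and 47 − 19 = 28 to complete. It concerns the primary rating and does not bear on this point. The figure that does is the planned loss from 31 dispensed to 28 completing: 3/31 = 9.7%.

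**Do the tests drop incomplete rows?** Both were tried on simulated data for 28 participants.
- Friedman, 28 × 3 = 84 cells, one removed: no result was returned. With omission switched on, the statistic was identical to that from the 27 complete participants.
- RMANOVA, 28 × 2 lenses × 2 visits = 112 cells, one removed: the procedure refused to run because the data were unbalanced. The participant must be removed or the value filled in, and the plan rules out filling in.

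**At-home forms.** The documents give no missed-form rate, so m is assumed, independent across forms. Share of participants lost from one lens's three-day test = 1 − (1 − m)³. Expected complete participants out of 28 = 28 × (1 − m)³.

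| m per form | Share lost | Complete of 28 |
|---|---|---|
| 1% | 1 − 0.99³ = 3.0% | 27.2 |
| 3% | 1 − 0.97³ = 8.7% | 25.6 |
| 5% | 1 − 0.95³ = 14.3% | 24.0 |
| 10% | 1 − 0.90³ = 27.1% | 20.4 |

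**Lens fit.** Assume RMANOVA is run over lens by visit. Section 5.3 says Visit 4 is normally combined with Visit 3. A participant who leaves between Visits 4 and 5 then has dispense and 1-week fit for the first lens and dispense fit for the second: three of four cells, with both dispense values. All three are lost to the test. Someone who leaves before Visit 4 has data on one lens only, so no lens contrast is discarded. From planned attrition, the avoidable loss is therefore at most 3/31 = 9.7%, reached only if all three leave between Visits 4 and 5.

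**The case against.** The strongest reply is that nothing in Section 12.1 is broken. A reader might infer a flat contradiction between the inclusion sentence and Table 6. But that sentence, read to its end, governs who may be removed by decision. Beside the rule against extrapolation, it is compatible with ordinary available-case practice: everyone is in the population and each test uses the values it can. Read literally as a promise about every test, it would also be broken by the paired t-test and Wilcoxon whenever one value of a pair is missing. This objection stands, and the point is not put as a contradiction.

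A reader might also infer a Friedman test over all six forms, where the same formula gives losses of 17%, 26% or 47% at 3%, 5% or 10% missed. The documents do not support it: Section 12.1 describes the time comparison as within one lens, so three forms is the right count.

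Three further limits stand:
- The lens-by-visit RMANOVA is the natural layout for outcomes measured at dispense and 1 week, but Table 6 does not state it. As extracted, the table also does not show with certainty which test serves which row.
- Independence tends to overstate the loss, because misses that cluster in a few people remove fewer participants. Section 6 says adherence to rating time windows is monitored, and some text around form collection is not visible.
- The recorded values are not thrown away altogether. They still enter the descriptive statistics and the pairwise tests.

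The reply does not show that the repeated-measures tests keep incomplete participants, or that another method is named. That Table 6 is only anticipatory leaves room for a better method but does not choose one.

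**Conclusion.** The point holds as a minor defect of efficiency and specification. It affects the at-home time comparisons and the secondary fit outcomes. The two primary outcomes are a single 1-week rating per lens, so a missed form does not touch them, nor does it touch pairwise Wilcoxon or paired t-tests that do not use that day.

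For the forms, the loss runs from about 3% to 27% of participants per three-day test, on assumed miss rates of 1% to 10% and independence. For fit, it is at most 9.7%, on the inferred four-cell layout and the least favourable timing of dropout.

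A reader might infer that the complete-row results are biased whenever people with gaps differ from the rest. That is too strong. In a within-person comparison, a different overall level does no harm; bias arises when missingness relates to the within-person lens or time difference. The documents allow that but do not establish it.

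**What to change.** In Table 6:
1. For the continuous variables (movement, acuity, NITBUT), replace RMANOVA with a linear mixed model: random participant; fixed lens, visit and lens-by-visit; REML on all recorded data. It keeps the incomplete participants and needs only a missing-at-random assumption.
2. For the Day 1, 3 and 5 ratings, keep the rank approach, and use Skillings-Mack when a day is missing. It equals Friedman with complete data. It still omits anyone with only one recorded day. A linear model on bounded 0–10 integer ratings is not proposed: it would swap a rank test for a comparison of means and would not give the same results even with complete data.
3. Keep Wilcoxon and the paired t-test for two-lens contrasts at one visit.
4. Report N for each test.

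The mixed model does not cover centration, which is an ordered four-category grade, or the redness and staining variables; for these, item 4 at least shows how many participants each result rests on.

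The cost is a change of wording and slightly more modelling work. No new data are needed. With complete data, the mixed model gives the same estimated lens and visit contrasts as RMANOVA.

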5.3 SCHEDULED AND UNSCHEDULED VISITS

This study has 5 visits. The visits are as follows:

- **Visit 1:** Screening, baseline assessments, fitting of both study lenses.
- **Visit 2:** Dispense lens type #1 (normally combined with Visit 1)
- **Visit 3:** 1-week follow-up assessment of lens type #1 (6 to 10 days after Visit 2), [REDACTED]
- **Visit 4:** Dispense of lens type #2 (normally combined with Visit 3)
- **Visit 5:** 1-week follow-up assessment of lens type #2 and study exit (6 to 10 days after Visit 4), [REDACTED]

A scheduled follow-up visit may only take place when the participant attends wearing the study lenses for 6-8 hours. If this is not the case and the participant is not experiencing any problems with the lenses, the appointment will be rescheduled, ideally within the visit window.

Visits that fall outside of the specified visit windows will be designated as protocol deviations and at the end of the study, the data collected during protocol deviations will be assessed for their suitability to be included in the analysis population.

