8 ADVERSE EVENTS

See CORE SOP012_v02 for a description of all adverse events, including management and reporting. An 'adverse event' refers to any undesirable clinical occurrence in a participant, whether

it is considered to be device-related or not. Adverse events (AE) may be classified as ‘unanticipated adverse device effects,’ ‘serious adverse events,’ ‘significant adverse events,’ or ‘non-significant adverse events,’ as defined below, Table 4.

A number of conditions may result in temporary suspension until resolution. These include corneal infiltrates, corneal staining, limbal injection, bulbar injection or tarsal conjunctival abnormalities.

Table 4: Classification of types of adverse event

Classification	Definition
Serious Adverse Event	Those events that are life-threatening, or result in permanent impairment of a body function, or permanent damage to a body structure or necessitate medical (therapeutic) or surgical intervention to preclude permanent impairment of a body function or permanent damage to a body structure.
Significant Adverse Event	Those non-serious adverse events that occur with contact lens usage that are not sight-threatening but are usually symptomatic and may warrant therapeutic management and /or temporary or permanent discontinuation of contact lens wear.
Non-Significant Adverse Events	Those less severe non-serious adverse events that occur with contact lens usage that are not sight-threatening, may or may not be symptomatic and may warrant palliative management, such as ocular lubricants or temporary interruption of contact lens wear.
Unanticipated Adverse Device Effect	Adverse events in a study that were not previously identified in the protocol in terms of nature, severity, or degree of incidence. An Unanticipated Serious Adverse Device Effect is an unanticipated adverse event that is serious in nature and caused by or associated with the device and is considered reportable.

AE classification, coding (for reporting to the sponsor) and reporting details, plus examples, are provided in Table 5.

Table 5: Contact lens adverse event classification, coding and reporting guide

Code	Condition	Reporting
Serious Adverse Events		
01	Presumed infectious keratitis or infectious corneal ulcer	For all serious AEs: Notify sponsor as soon as possible, within 24 hours;
02	Permanent loss of ≥ 2 lines of best spectacle corrected visual acuity (BSCVA)	
03	Corneal injury that results in permanent opacification within central cornea (6mm)	

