04	Uveitis or Iritis (e.g. presence of anterior segment inflammation as described in ISO 11980, Annex B)	

05	Endophthalmitis	ORE reporting will be within 24 hours as per requirements
06	Hyphema	
07	Hypopyon	
08	Neovascularization within the central 6mm of cornea	
00	Other serious event	
Significant Adverse Events		
11	Peripheral (outside central 6mm), non-progressive, non-infectious ulcer	Notify sponsor as soon as possible, within 5 working days ; ORE reporting as per requirements
12	Symptomatic corneal infiltrative event	
13	Superior epithelial arcuate lesions (SEALs) involving epithelial split	
14	Corneal staining \geq dense coalescent staining up to 2mm in diameter (e.g. moderate, ISO 11980 grade 3)	
15	Corneal neovascularization \geq 1.0mm vessel penetration (e.g. \geq ISO 111980 Grade 2), if 2 grade change from baseline	
16	Any temporary loss of \geq 2 lines BSCVA for \geq 2wks	
17	Any sign and/or symptom for which participant is administered therapeutic treatment or which necessitates discontinuation of lens wear for \geq 2 weeks	
10	Other significant event	
Non-significant Adverse Events		
21	Conjunctivitis (bacterial, viral or allergic)	Notify sponsor as soon as possible, within 5 working days ; ORE reporting as per requirements
22	Papillary conjunctivitis if \geq mild scattered papillae/follicles approximately 1mm in diameter (e.g. ISO 11890 Grade 2), if 2 grade change from baseline	
23	Asymptomatic corneal infiltrative events	
24	Any sign and/or symptom for which temporary lens discontinuation for $>$ 1 day is recommended (if not already classified)	
20	Other sign and/or symptom warranting classification as a non-significant adverse event	

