9 DISCONTINUATION FROM THE STUDY

Participants discontinued from a study will be reimbursed \$20 per hour for their active involvement in the study (including the initial screening visit). Participants will be discontinued at the discretion of the investigator or sponsor in consideration of participant safety or protocol compliance, or at discretion of the participant. The following is a list of possible reasons for discontinuation from the study:

- Screening failure: Participants will be discontinued if they do not meet the inclusion and exclusion criteria outlined in section 5.1.3.
- Unacceptable performance with products to be used in study: Participants may be discontinued if they are unable to achieve acceptable comfort and /or vision with the study products.
- Positive slit lamp finding: Participants may be permanently discontinued from the study depending on the severity of the condition and on the judgement of the investigator.
- Adverse event: If a participant experiences an adverse event during the study they may be discontinued based on the clinical judgement of the investigator.
- Symptoms: If the participant has persistent symptoms they may be discontinued based on the clinical judgement of the investigator.
- Disinterest, relocation or illness: The participant may choose to discontinue due to reasons within or beyond their control.
- Violation of protocol or non-compliance: The participant will be discontinued if they are unable or unwilling to follow the protocol specified visit schedules and/or study procedures.
- Instillation of topical ocular medication: The participant will be discontinued if they elect to use a topical ocular medication during the study unless that topical ocular medication is prescribed for a limited duration (less than two weeks) to treat a transient condition; in this case the participant may remain an active participant (at the discretion of the investigator) after stopping topical ocular medication following resolution of the ocular condition).
- Lost to follow-up: The participant will be discontinued if they cannot be contacted and do not return for a final exit visit, and if the investigator has made a reasonable effort to contact the participant for a final study visit.
- Premature termination of the study by the sponsor, CORE or the Office of Research Ethics at the University of Waterloo.

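### Section 12.1 lets evaluated participants be removed for any protocol deviation or adverse event, without criteria, a masked pre-lock decision, or a retained analysis of everyone

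*Combined protocol and SAP*

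**What the plan says.** Section 12.1 begins from a sound default: "All participants who were evaluated will be included in the analysis". It then makes an exception, "unless their removal is agreed by the sponsor due to protocol deviations and/or adverse events". The visible text does not say which deviations or events qualify, who proposes a removal, when it is decided, or whether those deciding know the lens sequence. The sentence shows no redaction.

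Section 8 defines an adverse event broadly: it "refers to any undesirable clinical occurrence in a participant", whether or not the device is the cause. Section 5.3 adds a second route. For visits outside their window, at the end of the study "the data collected during protocol deviations will be assessed for their suitability to be included in the analysis population", again without criteria.

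Several other provisions bear on the point:

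- **Masking.** Section 4.1.3 keeps study investigators masked to the randomisation schedule until lock. It does not mention the sponsor or the analysts. Section 4.1.4 concedes that investigator masking may be incomplete.
- **Analysis.** Section 12.1 states: "Unmasked data analysis will be conducted using Statistica, SPSS, or other appropriate software".
- **Deviation classes.** Section 15.4 separates major from minor deviations for reporting to the ethics office. It does not tie either class to exclusion from the analysis.
- **Transparency.** Sections 9 and 15.4.3 put all discontinuations and deviations in the final report.
- **Withdrawal.** Section 9 lets participants who choose to leave withdraw their data.

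No section defines a full analysis set, a per-protocol set, or a sensitivity analysis that restores removed participants.

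**The concern.** Each participant rates both lenses, and the comparison rests on within-person differences. If people who have an event tend to score one lens worse, dropping them moves the mean difference in favour of that lens, even if nobody intends it. An exclusion rule that depends on something happening after randomisation, and possibly because of the lens, is therefore not neutral in the way a baseline eligibility rule is.

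With about 28 completers, one removal is 1/28 = 3.6% of the data. The final report would show that a deviation or discontinuation occurred, but not what the result would have been with that person included. A reader could not tell a harmless removal from one that changed the conclusion.

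**Working it through.** **1. The plan's own figure.** Section 5.1.1 gives a difference of 0.8, SD 1.9, 80% power and two-sided alpha 0.05. Taking 1.9 as the SD of within-person differences, the normal approximation is ((1.960 + 0.842) × 1.9 / 0.8)² = 44.3, so 45. The exact paired t-test gives 47 (power 80.7%), which matches the plan. Then 47 − 19 pilot completers = 28 for this study. Section 12.1 does not say whether the pilot data are pooled, so both 28 and 47 are shown. With 28 alone and nobody removed, power is about 57%.

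**2. Event counts.** The only rate in the documents is the 0.035% infection incidence in section 7, with no time base: 31 × 0.00035 = 0.011 infections. It does not give the total number of adverse events. I therefore assume 0.5, 1 or 2 expected events. The chance of at least one removal if every event leads to removal is 1 − (1 − m/28)^28, which is 40%, 64% and 87% for m = 0.5, 1 and 2.

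**3. Handling ratings: scenario only.** Let d be the rating of the event-linked lens minus the other, normal with SD 1.9 and mean μ = −0.8 (or 0 for type I error). The event probability is logistic in (μ − d)/1.9, with odds ratio 2 to 5 per SD worse rating and the intercept set to give the expected count. Everyone with an event is removed, and a paired t-test is run on the rest. Results by simulation, ranges running from odds ratio 2 to 5:

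| Expected events | Estimate of a true 0.8 deficit, n=28 | Power, n=28 | Type I, n=28 | Estimate, n=47 | Type I, n=47 |
|---|---|---|---|---|---|
| none removed | 0.80 | 57% | 5.0% | 0.80 | 5.0% |
| 0.5 | 0.78–0.75 | 54–53% | 5.0–5.2% | 0.786–0.770 | 5.1–5.2% |
| 1 | 0.75–0.70 | 52–48% | 5.2–5.7% | 0.772–0.741 | 5.1–5.5% |
| 2 | 0.71–0.62 | 46–40% | 5.5–7.6% | 0.745–0.689 | 5.4–6.7% |

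The Wilcoxon test that Table 6 lists for ratings behaves alike at n = 28: type I error 5.3–5.9% with one event and 5.7–7.5% with two.

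Three milder scenarios at n = 28:

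- **Events unrelated to ratings (odds ratio 1).** The estimate stays at 0.80 and type I error at 5%. Power is 56%, 56% and 54% for 0.5, 1 and 2 events.
- **Only half of events lead to removal.** With two expected events, type I error is about 5.0–5.6%.
- **Events follow a poor rating of either lens equally.** Type I error stays at about 5%. Some shrinkage remains, to between about 0.78 and 0.70 with two events.

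**4. Corneal staining: the documented link.** Table 6 compares between lenses a group that includes "limbal, bulbar and tarsal redness; corneal and conjunctival staining". Table 5, code 14, makes staining at or above "dense coalescent staining up to 2mm in diameter" (its example is ISO grade 3) a significant adverse event. A high staining score is thus itself a possible ground for removal. One grade 3 score with one lens against grade 0 to 1 with the other contributes 3/28 = 0.11 to 2/28 = 0.07 grade to the mean difference, and removal deletes all of it. This assumes that the trial scale, which is not visible, resembles the ISO grades. It also requires the event to be in an analysed eye. Section 12.1 allows right-eye-only analysis and names biomicroscopy as an example; in that case a left-eye event contributes nothing.

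**The case against.** The other side has a fair case. The default is inclusion, removal needs agreement, and deviations and discontinuations are reported. Both lenses are approved, each is worn for about a week, and section 7 calls the study minimal risk, so events may be few. The calculations on ratings assume the event count, a link to one lens and removal of every event; none of these comes from the documents. Section 10 even says that subjective responses on handling do not count as complaints or malfunctions. The one documented example, staining, is neither a primary nor a listed secondary outcome and depends on which eye is analysed. Some participants would leave the paired comparison whatever section 12.1 said, since under section 9 "If a participant experiences an adverse event during the study they may be discontinued based on the clinical judgement of the investigator"; those who stop before rating both lenses cannot be charged to this clause.

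All of that stands, and it limits the size of the point. It does not remove it. Masking investigators until lock does not bind whoever agrees removals, and reporting who deviated is not the same as reporting the result with them included.

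A reader might go further and infer that the sponsor will choose exclusions knowing the lens codes or the results. The documents do not support that. The word unmasked in section 12.1 describes the data analysis, not the removal decision, and nothing shows the sponsor holding lens codes. An end-of-study judgement under section 5.3 is compatible with a masked review before lock. The fault is that no such review is required.

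**Conclusion.** The point holds as a defect in the rule, with a modest and conditional effect. Section 12.1 permits removal on a ground that may follow from treatment, without criteria, timing, masking or a retained full result. The omission is certain; its consequence is not. With 0.5 to 1 expected event the effect on the handling comparison is small even under a one-lens link. It becomes noticeable at two events with a strong link and full removal, and it is smaller if 47 are analysed. If events are unrelated to ratings, the only cost is one to three points of power.

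It would be wrong to read this as showing that the primary result will be biased, because no link between adverse events and handling ratings is documented. Nor should one quote the inflation that would follow from deliberately deleting the one, two or three least favourable ratings (about 8%, 14% or 23% type I error at n = 28). That is a theoretical bound, and nothing in the documents suggests such a practice.

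**What to change.** Replace the sentence in section 12.1 with wording to this effect:

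> The main analysis of each outcome includes all randomised participants with the data needed for that comparison (for the primary outcomes, a 1-week handling rating for both lenses), except data withdrawn under section 9. An adverse event is not a reason for removal from the analysis. Exclusions for major deviations listed in advance are decided by staff masked to lens before database lock, and are used only in a sensitivity analysis reported beside the main one.

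Make the out-of-window sentence in section 5.3 refer to this rule. Report, by lens, the number of participants who discontinue before rating both lenses, with reasons. None of this alters who stops lens wear or leaves the study.

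The cost is SAP wording, a short list of qualifying deviations, one further analysis run and one table; the planned sample size does not change. There are two downsides. Some off-window or otherwise deviating data stay in the main analysis. The main set still needs both ratings, so early discontinuations are made visible but not recovered.
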